3.2 Secondary objectives

- 1. To determine the overall survival of patients treated with Axitinib
- 2. To determine the progression free survival of patients treated with Axitinib
- 3. To determine the disease control rate at 16 weeks and response rate as defined by Choi Criteria
- 4. To determine the duration of response (as defined by Choi Criteria) of patients treated with Axitinib
- 5. To assess the toxicities associated with the treatment of Axitinib of patients treated with Axitinib

4. STUDY DESIGN:

This study will be a prospective, single-institution, single-arm phase II study of Axitinib in patients with unresectable recurrent and metastatic head and neck squamous cell carcinoma with ECOG performance status 0-2, for recurrent or metastatic head and neck cancer. The subjects will be started on treatment with 5 mg of Axitinib twice a day continuously, with subsequent dose escalation to 7 mg and then 10 mg twice a day in the absence of grade 2 or worse toxicities. This will be followed by clinical and/or radiologic response assessment after 8 weeks and subsequently every 2 months until disease progression (defined per Choi criteria, or obvious progression on clinical or laryngoscopic/endoscopic exam) or intolerable toxicity (defined as below). Patients with confirmed progressive disease who, in the investigator's opinion, continue to receive benefit from Axitinib treatment and who meet the criteria for treatment may continue to receive treatment as described in Section 8.3. Axitinib should be discontinued if there is further evidence of progression defined as an additional 10% or greater increase in tumor burden volume from time of initial progression (including all target lesions and new measurable lesions).

During treatment on this protocol, all patients will be evaluated for safety as detailed below.

5. STUDY POPULATION:

5.1. Stage:

Unresectable, recurrent or metastatic squamous cell carcinoma of head and neck.

5.2. Inclusion Criteria:

1. Histologically documented squamous cell head and neck cancer with or without metastases, not amenable to curative treatment; or the patient has documented refusal of curative treatment.

2. Presence of measurable disease by CT scan or

a. for cutaneous squamous cell carcinoma not present on CT imaging but present on physical exam with lesion(s) greater than >/= 10mm

b. patients with non-target lesions are permissible per PI discretion

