The response to treatment will be assessed clinically at each visit, as well as by appropriate radiologic imaging, starting at 8 weeks +/- 2 weeks and then at 8-week intervals, +/- 2 weeks. Tumor response to therapy will be interpreted by Choi Criteria with interpretation performed by UMCC Tumor Response and Assessment Core. Patients will be taken off trial for significant side effects, per patient preference, or for noncompliance with treatment plan. Beyond progression, survival will be assessed every 12 weeks. Patients will also be followed for 28 days after cessation of study participation for safety monitoring. Patients with confirmed progressive disease who, in the investigator's opinion, continue to receive benefit from Axitinib treatment and who meet the criteria for treatment may continue to receive treatment as described in Section 8.3. Axitinib should be discontinued if there is further evidence of progression defined as an additional 10% or greater increase in tumor burden volume from time of initial progression (including all target lesions and new measurable lesions).

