For statistical analysis that include the investigator-assessed progression date, subjects who continue treatment beyond investigator-assessed, Choi Response defined progression will be considered to have investigator-assessed progressive disease at the time of the initial progression event.

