9. RESPONSE CRITERIA

The Choi Criteria will be used to assess tumor response to therapy. Interpretation will be performed by centralized UMCC Tumor Response and Assessment Core (TRAC). If density measurements are not available and cannot be accurately measured by photography or imaging, response can be dictated by measurement alone (i.e.for cutaneous squamous cell carcinomas that are not visualized on CT scan but are measurable on physical exam only). Non-target lesions are also permissible in which case overall assessment would be limited to complete response, stable disease, and progressive disease.

Complete Response:

- Disappearance of all lesions
- No new lesions

Partial Response:

- A decrease in size¹ of $\ge 10\%$ or a decrease in tumor density (HU) $\ge 15\%$ on CT
- No new lesions
- No obvious progression of non-measurable disease

Stable Disease

- Does not meet the criteria for CR, PR, or PD
- No symptomatic deterioration attributed to tumor progression

Progressive Disease

- An increase in tumor size of \geq 10% and dose not meet criteria of PR by tumor density (HU) on CT
- New lesions
- New intratumoral nodules or increase in the size of the existing intratumoral nodules
- ¹⁻ The sum of longest diameters of target lesions as defined in RECIST

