Overall and progression-free survival rates at 2, 4 and 6 months will be reported along with 95% confidence intervals based on the binomial distribution. Kaplan-Meier methods will also be conducted to estimate these rates and the medians of PFS and overall survival (OS) of the 37 evaluable patients, with a corresponding standard error estimate based on Greenwood's formula (53).

Among this cohort of patients, progression will be determined based on Choi critieria.

- To determine the response.

The best overall response rate will be determined for each evaluable patient at 8 and 16 weeks following the start of Axitinib. The proportion of evaluable patients who have an objective response (complete or partial) and stable disease will be calculated, and a 95% exact binomial confidence interval will be determined.

- To determine the toxicity profile of this treatment regimen.

The proportion of treated patients experiencing any clinically significant (Grade 3 or worse) toxicity will be determined, with a 95% exact binomial confidence interval; specific toxicities of all grades will be tabulated.

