14.3. Efficacy Analysis

Efficacy analysis will include Progression-free survival (PFS), Overall response rate (ORR), including complete (CR) and partial response (PR), stable disease, disease control rate (CR+PR+stable disease) at 16 weeks, along with overall survival (OS).

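### The plan does not settle whether 16-week disease control means best response so far or status at week 16, and neither section excludes patients who have already progressed

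*Combined protocol and SAP*

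**What the plan says.** Three places in the combined protocol and SAP bear on this endpoint.

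- Section 3.2, objective 3: "To determine the disease control rate at 16 weeks and response rate as defined by Choi Criteria".
- Section 14.3 gives the components and the time point, without the word best: "disease control rate (CR+PR+stable disease) at 16 weeks".
- Section 13.4 gives the computation: "The best overall response rate will be determined for each evaluable patient at 8 and 16 weeks", counted from the start of axitinib. It continues: "The proportion of evaluable patients who have an objective response (complete or partial) and stable disease will be calculated", with an exact 95% binomial interval. It does not name disease control.

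Three other provisions determine how a patient would be classified.

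- Section 9 defines stable disease by exclusion, with no minimum duration: "Does not meet the criteria for CR, PR, or PD" (and no symptomatic deterioration from tumour progression).
- Section 7.1 sets imaging "starting at 8 weeks +/- 2 weeks and then at 8-week intervals, +/- 2 weeks".
- Section 8.3 allows axitinib to continue after a first Choi progression. Such patients are "considered to have investigator-assessed progressive disease at the time of the initial progression event", but that sentence is limited to analyses that use the progression date.

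**The concern.** Best overall response ordinarily means the best category recorded up to a given time. On that meaning, a patient who is stable at week 8 and progressed at week 16 has a best response of stable disease and enters the numerator. That is not disease control at 16 weeks.

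Treatment past progression raises a second problem. A patient who meets Choi progression at week 8 may still be on axitinib and scanned at week 16. Choi allows a partial response on density alone, so a patient called progressed on size at week 8 could be scored as responding or stable at the next scan. Nothing in section 13.4 or 14.3 removes that patient from the numerator.

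The trial is open label and single arm, and the investigators have already used this kind of measure as evidence of activity: section 1.2 cites the predecessor's disease control rate of 76.7% among the signs of efficacy in a trial that stopped for futility on 6-month PFS. A rate labelled as 16-week control should mean that, and its definition should be fixed before the data are seen.

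**Working it through.** **The plan's own figure.** No target, expected rate or sample size is stated for disease control. The only design figure is for the primary endpoint (section 13.2): 37 patients, 80% power, 70% against 50% alive at 6 months, upper-tailed 5% test. The exact binomial calculation reproduces it. With n = 37 and success declared at 24 or more alive, the type I error is 0.0494 and the power 0.807; 37 is the smallest n that meets both limits. Disease control does not enter this calculation.

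**How three patients would be scored**

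| Week 8 | Week 16 | Best response through week 16 | Status at week 16 | Status at week 16, no earlier PD |
|---|---|---|---|---|
| SD | SD | controlled | controlled | controlled |
| SD | PD | controlled | not controlled | not controlled |
| PD, treatment continued | SD or PR | not settled by the text | controlled | not controlled |

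Row two is where the usual reading of 13.4 and the status reading of 14.3 part. Row three is a gap under both sections, because neither states that an earlier progression rules out later control.

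**Size per patient.** Taking all 37 as evaluable, each patient scored differently moves the rate by 1/37 = 2.7 points.

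**Illustration by count.** Assume 28/37 = 75.7% counted as controlled on best response, close to the predecessor's 76.7% (23/30). The exact 95% interval is 58.8% to 88.2%. Removing patients who had progressed by week 16 gives:

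- 2 removed: 26/37 = 70.3% (53.0% to 84.1%)
- 4 removed: 24/37 = 64.9% (47.5% to 79.8%)
- 6 removed: 22/37 = 59.5% (42.1% to 75.2%)
- 10 removed: 18/37 = 48.6% (31.9% to 65.6%)

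**Illustration from the predecessor's PFS.** Section 1.2 gives a median PFS of 3.7 months (95% CI 3.5 to 5.7). In weeks, 3.7 × 30.4375/7 = 16.09. Assuming exponential progression, the proportion progression-free at week t is 0.5^(t/median):

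- Week 8: 0.5^(8/16.09) = 70.8%, or about 26 of 37.
- Week 16: 0.5^(16/16.09) = 50.2%, or about 19 of 37.
- Difference: about 21 points.

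At the ends of the interval, a median of 3.5 months (15.22 weeks) gives 69.5% and 48.3%, a gap of 21 points. A median of 5.7 months (24.78 weeks) gives 80.0% and 63.9%, a gap of 16 points. These are RECIST v1.0 data under a smooth curve. They show that the definition can matter, but they do not estimate the gap under Choi. The predecessor's Choi disease control rate is not used as a base because Table 4 prints 80.8% while its counts give (19 + 2)/29 = 72.4%.

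**The case against.** A reader might infer that the plan has settled on best overall response for 16-week disease control, and so will overstate it by about 21 points. The documents do not support that.

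- Section 13.4 never names disease control. Objective 3 and section 14.3 do name it, both attach the time point, and neither says best.
- The two weeks named in 13.4 match the first two scheduled scans, so the sentence can also mean the response at each scan. No carry-forward rule is written.
- The 21 points come from applying a RECIST median to a Choi endpoint, in a protocol that argues RECIST misread progression in that cohort. Progression is found largely at scheduled scans, so a smooth exponential curve gives false precision near week 16. The calculation also treats all 37 as evaluable.
- Section 13.4 also reports PFS at 4 months (17.4 weeks) with progression by Choi. A reader would therefore see the proportion progression-free close to week 16 beside the disease control rate.
- The only fixed comparator in the plan is 50% alive at 6 months. Disease control has no null value, test or success rule.

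All of this stands, and it limits the point to a conflict and a gap in the definition. It does not remove them. The one stated computation, on its usual meaning, gives a different quantity from the one named in the objective. The more favourable status reading still leaves the patient with earlier progression unassigned. The 4-month PFS figure helps a careful reader but does not define this endpoint.

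**Conclusion.** The point holds as a matter of definition. Sections 13.4 and 14.3 do not agree on whether 16-week disease control is cumulative best response or status at week 16. Neither excludes a patient who progressed by Choi at week 8, continued treatment and was later scored stable or responding.

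The firm size is 2.7 points per affected patient, assuming 37 evaluable. The number of such patients under Choi cannot be derived from the documents; the gap of 16 to 21 points is a RECIST-based illustration only. The endpoint is secondary and descriptive, so the 37 patients and the primary test of 6-month survival are untouched.

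**What to change.** In section 13.4, define 16-week disease control as: alive, with CR, PR or SD by Choi at the week-16 (+/- 2 weeks) assessment, and no Choi progression at or before that assessment, whether or not treatment continued. Report best overall response as a separate quantity, and have section 14.3 refer to this definition.

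State how a missing week-16 scan is handled. One option is to count it as not controlled in the main figure and add a sensitivity analysis among patients with a scan. The rule should cover patients who leave axitinib because their disease has become amenable to curative treatment, since section 10 keeps them in the efficacy analysis.

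The core change is one sentence, with a second for missing scans. It needs no new data, visits or patients. The downside is that the reported rate may be lower.

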8.2.4. Dose Interruption and Reductions

Adverse events and other symptoms will be graded according to the current Common Terminology for Adverse Events version 4.03 (CTCAE v4.03). This section contains management of adverse events except hypertension, hemoptysis and proteinuria which are discussed in subsequent sections.

Patients developing a treatment-related CTCAE Grade 1 or 2 adverse event will have their dose continued at the same dose level. Patients developing a treatment-related CTCAE Grade 3 or above adverse event will have dose reductions as described below.

Treatment delays due to drug-related toxicity > 2 weeks will result in discontinuation of treatment. Patients removed from treatment for intolerable toxicity will still be followed for survival.

The criteria for dose modification for study drug related adverse events is summarized Table 8 below.

Table 8. Criteria for Dose Modification for Axitinib Related Adverse Events other than Hypertension, Hemoptysis, or Proteinuria

Related Adverse Events	Intervention
Grade 1	Continue at same dose level
	May escalate dose per protocol
	Manage toxicities as medically necessary
Grade 2	Continue at same dose level
	Manage toxicities as medically necessary
Grade 3 nonhematologic	Decrease dose to one lower dose level
drug-related toxicity	Manage toxicities as medically necessary
	Treatment may be interrupted up to 2 weeks per investigator discretion
Grade 4 nonhematologic drug-related toxicity or Grade 4 hematologic toxicity*	Interrupt dosing (up to 2 weeks); re-start at one lower dose level as soon as improvement to CTCAE Grade 2. If patient requires dose reduction below 2 mg BID, discontinue trial participation. Manage toxicities as medically necessary
*Patients who develop grade 4 lymphopenia may continue study treatment without interruption.	

Guidelines for dose reductions for specific adverse events are provided in the following sections.

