12. ADVERSE EVENT REPORTING

12.1. Adverse Events

All observed or volunteered adverse events regardless of suspected causal relationship to Axitinib will be reported as described in the following sections.

For all adverse events the investigator must pursue and obtain information adequate both to determine the outcome of the adverse event and to assess whether it meets the criteria for classification as a serious adverse event requiring immediate notification to Pfizer, Inc. or its designated representative. For all adverse events sufficient information should be obtained by the investigator to determine the causality of the adverse event. The investigator is required to assess causality. For adverse events with a causal relationship to Axitinib, follow-up by the investigator is required until the event or its sequelae resolve or stabilize at a level acceptable to the investigator, and Pfizer, Inc. concurs with that assessment.

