12.5. Serious Adverse Events

A serious adverse event or serious adverse drug reaction is any untoward medical occurrence at any dose that:

- Results in death;
- Is life-threatening (immediate risk of death);
- Requires inpatient hospitalization or prolongation of existing hospitalization;
- Results in persistent or significant disability/incapacity;
- Results in congenital anomaly/birth defect.

Progression of the malignancy under study (including signs and symptoms of progression) should not be reported as serious adverse events unless the outcome is fatal during the trial or within the safety reporting period. Hospitalizations due to signs and symptoms of disease

progression should not be reported as serious adverse events. If the malignancy has a fatal outcome during the study or within the safety reporting period, then the event leading to death must be recorded as an adverse event and as a serious adverse event with CTC grade 5 (See Severity Assessment). Medical and scientific judgment should be exercised in determining whether an event is an important medical event. An important medical event may not be immediately life-threatening and/or result in death or hospitalization. However, if it is determined that the event may jeopardize the subject and may require intervention to prevent one of the other outcomes, the important medical event should be reported as serious. Examples of such events are intensive treatment in an emergency room or at home for allergic bronchospasm; blood dyscrasias or convulsions that do not result in hospitalization; or development of drug dependency or drug abuse.

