13. STATISTICAL METHODS

13.1. Primary Objectives:

The primary aim of this study is to compare 6-month overall survival after treatment with Axitinib in patients with unresectable, recurrent or metastatic head and neck cancer to historical rates. Based on results in the literature, we assume a 6-month mortality rate of **50%** under current standard care in this patient population (11, 52). We will test whether survival after treatment with Axitinib is improved to 70% at 6-months compared to 50%.

Overall survival will be determined from the date of treatment initiation to date of death from any cause. For the primary endpoint, patients that are alive at 6 months following the initiation of study treatment will be considered successful. All other patients will be considered unsuccessful. Patients will be considered evaluable for the primary endpoint if they receive any dose of Axitinib.

13.2. Sample size justification:

We will enroll 37 additional patients for comparison of overall survival. Based on historical data, 6 month OS in heavily pretreated patients such as those included in this study is 50%. Thirtyseven patients will provide 80% power to detect a meaningful difference in proportion alive at 6months (70% vs 50% historically) with a type I error rate of 5%. For the primary endpoint of overall survival we anticipate no missing data and will test whether the proportion alive at 6 months is greater than the historical rate of 50% with an upper tailed test of binomial proportion.

Based on our prior experience at the University of Michigan, we anticipate accrual of approximately 4 patients every 5 months. With this rate of accrual, we can enroll 40 eligible patients in 50 months. With a minimum follow-up of 6 month for each patient, the study will complete in about 56 months.

13.3. Stopping rules for futility:

As we observed considerable evidence of activity in UMCC 2011.053, we plan no interim analysis for futility with data collected in the expansion cohort B. Formal analysis of efficacy will be performed at trial completion.

13.4. Analysis plan:

- To estimate survival rates.

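### Does the grade 3 or worse toxicity rate in section 13.4 need a written causality rule and time window?

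*Combined protocol and SAP*

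**What the plan says.** Section 13.4, under its aim of describing the toxicity profile, commits to this: "The proportion of treated patients experiencing any clinically significant (Grade 3 or worse) toxicity will be determined, with a 95% exact binomial confidence interval". Toxicities of every grade are also tabulated. The denominator is not in doubt, because treated patients in 13.4 match the safety set in 14.2 (at least one dose). The numerator carries no attribution rule, no period and no rule for deaths from the cancer.

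The sections around it bear on the numerator as follows.

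- **Objective (3.2, item 5):** "To assess the toxicities associated with the treatment of Axitinib of patients treated with Axitinib".
- **Collection (12.1):** "All observed or volunteered adverse events regardless of suspected causal relationship to Axitinib will be reported". Section 12.8 then requires a causality judgement on each event, and an event of unknown cause is handled as related.
- **Cancer deaths (12.5):** where the cancer proves fatal while the patient is on study or safety reporting is still open, the rule reads "then the event leading to death must be recorded as an adverse event and as a serious adverse event with CTC grade 5".
- **Periods:** 7.1 keeps patients under safety follow-up for 28 days after they leave the study. 12.2 has events entered on the CRF from first dose to the final visit, and stops collecting non-serious events when another anticancer treatment begins. 14.2 applies a 28-day limit after stopping drug, but only to one listing of related deaths.
- **Reporting (14.2):** adverse events are tabulated, including by maximum severity and by relationship, and serious events are listed patient by patient.

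**The concern.** The estimate is the only safety figure in the plan with a confidence interval, and it serves a secondary objective. If it counts every recorded adverse event, 12.5 turns a death from the cancer into a grade 5 event, and disease mortality is then reported as toxicity of the regimen. If it counts related events only, those deaths drop out. Two analysts could work from the same data, both cite the text, and publish different rates.

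The period is equally open. A cancer death months after the last tablet is in or out depending on which section is taken to govern. In an open-label, single-arm trial the choice could be made after the data are seen. Tolerability also matters to the case for the drug: section 1.2 sets axitinib's low rate of severe toxicity against 82% for the first-line triplet.

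**Working it through.** **1. Inputs and the plan's own figure.** From 13.1 and 13.2: n = 37, 6-month survival 50% (historical) and 70% (target), one-sided 5% test. Rejecting with 24 or more of 37 alive gives P(X ≥ 24 | 0.5) = 0.0494 and P(X ≥ 24 | 0.7) = 0.807, so the stated 80% power reproduces. Nothing in this calculation uses toxicity. The documents give no expected grade 3 or worse rate.

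**2. Deaths by month 6.** 37 × 0.30 = 11.1 and 37 × 0.50 = 18.5. Section 14.1 counts death from any cause, so these are all-cause deaths. They are not a count of cancer deaths, and month 6 is not an adverse-event window in any section.

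**3. Extreme case.** Suppose every one of these deaths is recorded as grade 5 and no other event counts. The rate is then 11/37 = 29.7% (exact 95% CI 15.9 to 47.0) or 18/37 = 48.6% (31.9 to 65.6). On a related-only reading with no drug toxicity it is 0/37 (0 to 9.5).

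**4. With other severe events.** Let g be the assumed share of patients with another counted event and d the share who die. Under independence the combined rate is 1 − (1 − g)(1 − d).

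| g (assumed) | d = 0.30 | d = 0.50 | increase |
|---|---|---|---|
| 20% | 44% | 60% | 24 to 40 points |
| 40% | 58% | 70% | 18 to 30 points |
| 60% | 72% | 80% | 12 to 20 points |

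If every patient who dies already has another counted event, the increase is 0.

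**5. Window alone.** Assume that drug stops at progression, that PFS is exponential with median 3.7 months (the pilot value in 1.2), and that survival after progression is exponential, fitted to 70% or 50% alive at 6 months (rates 0.179 and 0.472 per month). Then 3.6 of 11.1, or 8.4 of 18.5, deaths fall within 28 days of stopping. The differences are 11.1 − 3.6 = 7.5 and 18.5 − 8.4 = 10.1 patients. Section 8.3, however, allows treatment beyond progression. With one further month on drug the differences fall to 4.5 and 4.8; with two, to 2.4 and 2.1. The model also has no deaths before progression and applies a RECIST-based PFS to a trial assessed by Choi criteria. It does not give a dependable count.

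**6. The wording side by side.** 13.4 speaks of the toxicity profile of the regimen, and objective 5 ties toxicities to treatment. Sections 12 and 14.2 use *adverse event* when they mean events of any cause. Table 8 in 8.2.4 concerns related events and, within it, writes grade 4 hematologic toxicity without a qualifier, so the bare word is used there for related events. The periods in 7.1, 12.2 and 14.2 govern a follow-up duty, CRF recording and one listing. They do not compete to define the 13.4 numerator.

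**The case for a change.** The best case for acting is that the protocol does not use *toxicity* consistently. Section 1.1.3 introduces a summary of observed axitinib toxicity, and the table that follows (Table 2) is headed as all-causality and has a grade 3+ column. Section 8.2.4 adds a qualifier when it wants one: "Treatment delays due to drug-related toxicity > 2 weeks will result in discontinuation of treatment". An analyst who wished to count everything could cite both. The causality term in the 14.2 death listing is also not the judgement defined in 12.8. The 14.2 tables describe events and do not give the per-patient rate with its interval.

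Six months is not a ceiling either. Section 13.2 says "With a minimum follow-up of 6 month for each patient, the study will complete in about 56 months". If *during the study* in 12.5 ran to that point, about 28 to 34 of 37 patients would be expected to have died (exponential survival with median 6 to 11.7 months, uniform accrual). A few sentences would settle the matter.

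Some of this stands. The sentence is silent, Table 2 leaves some ambiguity, and the causality terms in 14.2 and 12.8 differ. The rest is weaker. The widest reading of *during the study* rests on an accrual timeline that says nothing about recording adverse events, while 12.2 ends recording at the last visit and later survival checks can be made by phone. The qualifier argument from 8.2.4 is undone by the unqualified use in its own Table 8. The worry about choosing after the fact is limited by what 14.2 must show anyway: cancer deaths recorded under 12.5 are serious events, so they appear in the SAE listing and a reader can see whether they are in the rate.

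**Conclusion.** No change to the plan is called for. Section 13.4 leaves a definition unwritten, but its own wording and objective 5 make treatment-related events the natural reading. Section 12.8 supplies the causality field for every event, and 14.2 puts severity, relationship and serious events on display. An analyst following these sections would produce a sound and checkable safety report. The rate feeds no hypothesis, threshold or stopping rule, and the primary test (24 or more of 37, alpha 0.0494, power 80.7%) does not depend on it.

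The size of the effect cannot be fixed from the documents. The 11 to 18 deaths are all-cause deaths by month 6 at the design rates. How many would be cancer deaths, inside adverse-event recording, in patients with no other grade 3 or worse event is unknown and could be zero. The increase of 12 to 40 points holds only if all those deaths are counted, are independent of other severe events, and such events occur in an assumed 20% to 60% of patients. The window figure of 7.5 to 10.1 patients falls to between 2 and 5 once treatment continues one or two months past progression, so no weight should be put on it.
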